5.0 Inclusion and Exclusion Criteria/ Study Population

Inclusion criteria:

- 1) elevated depressive symptoms, defined as a score of ≥ 10 on the PHQ-9³⁶
- 2) ILLIC (as determined during manual chart review)
- 3) age 18+
- 4) currently own an iOS- or Android-compatible smartphone
- 5) report willingness to utilize a mobile app for the treatment of depressed mood (response of “yes” on yes/no item)
- 6) have a valid e-mail address that is checked regularly *or* have regular access to text messages (to access follow-up assessments)
- 7) English fluency

Exclusion criteria:

- 1) Severe cognitive impairment that precludes completion of informed consent
- 2) current suicidal ideation on the PHQ-9 at screening or final study eligibility, defined as a response ≥ 1 (several days) on item nine

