13.0 Risks to Subjects

This is considered a minimal risk study. Minimal risk means the probability and magnitude of harm or discomfort anticipated in the research are not greater in and of themselves than those ordinarily encountered in daily life or during the performance of routine physical or psychological examinations or tests. The potential risks in this study include those related to: a) depressive symptoms, b) clinical deterioration, c) confidentiality, d) potential data breach from the app database, and e) frustration. All risk mitigation strategies outlined have previously been approved by the MUSC IRB and implemented with success during our team's prior Moodivate evaluation trials.

a) Depressive symptoms: Depressive symptoms will be monitored via the PHQ-9. All participants will complete the PHQ-9 weekly online via a REDCap survey that is accessible via mobile phone web browsers. All participants will own smartphones. Thus, all participants should have access to the online PHQ-9 assessments.

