b) Clinical deterioration: Drs. [name], [name], and their research team will monitor participant PHQ-9 scores for possible clinical deterioration (i.e., increasing depressive symptoms and/or the development of suicidal ideation) throughout the course of the study as participants complete the PHQ-9 weekly. Clinical deterioration will be defined as an increase of 5 or more points on the PHQ-9 from the baseline PHQ-9 assessment or a response of "More than half the days" or "Nearly every day" on item 9 ("Thoughts that you would be better off dead, or thoughts of hurting yourself in some way") of the PHQ-9. Our team has developed real-time alerts in REDCap which alert the investigative team if a participant completes a PHQ-9 assessment and evidences clinical deterioration. This system was developed during our prior Moodivate evaluation studies and has now been implemented with success across multiple studies. In the event that a participant evidences clinical deterioration, [name], a licensed clinical psychologist, or other IRB-approved clinical personnel will contact the participant via phone and will provide referrals for local mental health resources for depression treatment. [name] (or other IRB-approved clinical personnel) will suggest that the participant seek treatment and then will follow-up with the participant via phone one week later. In the event that a participant reports suicidal ideation either during study screening or during subsequent assessments, [name] will complete a risk assessment with the participant via phone. [name] will query the participant for details regarding the suicidal ideation, including a likelihood of harming oneself imminently and a plan for committing

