Regarding user privacy while using Moodivate, users will create a username and password in order to login to their account without storing their true identity. In Moodivate, we will store a one-way hashed version of the patient's email address to support password reset and unique identification, but that identification will not be traceable back to the user's true identity. We will not store any personally identifiable information (e.g., first name, last name, email address, phone number) of users in our app database. We will use a HIPAA-compliant server protected by industry-standard safeguards to prevent unauthorized access. Since we are not associating patient health information with personally identifiable information there would not be a risk of unauthorized release of patient medical data in the event of a security breach. User personal information will be contained behind secured networks and will only be accessible by the investigators, who will have special access rights to such systems. In addition, all sensitive information users supply will be encrypted via Secure Socket Layer (SSL) technology. We will not sell, trade, or otherwise transfer personally identifiable information to outside parties. Our privacy policy will be available within the app for users to view at any time.

Protection against risk resulting from depressive symptoms includes the following: Regarding suicidal ideation and broader mental health concerns, [name], a licensed clinical psychologist, will take appropriate action as outlined by the MUSC IRB, NIH, and the State of South Carolina, which may include contacting the authorities and/or pursuing involuntary commitment at a mental health facility. If participants present no imminent danger but also need more extensive treatment of mental health concerns, they will be given appropriate referrals. As noted above, PHQ-9 data will be monitored over time in order to detect any possible clinical deterioration. PHQ-9 data will be monitored using only the participants' subject numbers. Should a participant evidence clinical deterioration, [name] will then use the participant database to obtain contact information for the participant based on their subject number.

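### A new PHQ-9 item 9 score of 1 at follow-up appears to call for a phone risk assessment, but the only real-time alert described does not cover it unless the total also rises by 5 or more

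*Combined protocol and SAP*

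**What the plan says.** Four parts of the combined protocol and SAP bear on this.

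- **Threshold for ideation.** Section 5.0, exclusion criterion 2, excludes people with "current suicidal ideation on the PHQ-9 at screening or final study eligibility, defined as a response ≥ 1 (several days) on item nine". No other section gives ideation a numerical threshold under that name.
- **Duty to assess.** Section 13.0 b) opens the risk-assessment procedure with "In the event that a participant reports suicidal ideation either during study screening or during subsequent assessments". A phone assessment of imminence and plan follows. The sentence gives no item 9 cut-off and no deadline.
- **Alert.** The same paragraph says "Our team has developed real-time alerts in REDCap which alert the investigative team if a participant completes a PHQ-9 assessment and evidences clinical deterioration". Clinical deterioration is defined there as "an increase of 5 or more points on the PHQ-9 from the baseline PHQ-9 assessment", or either of the two highest response options on item 9 (scores 2 and 3).
- **Mode of follow-up.** Section 13.0 a) says "All participants will complete the PHQ-9 weekly online via a REDCap survey". Section 10.0 sets four weekly follow-ups after a baseline completed following e-consent.

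Other monitoring is described in general terms. Section 13.0 b) has the team watch PHQ-9 scores for "increasing depressive symptoms and/or the development of suicidal ideation". Section 12.0 (Trial Safety) has staff report signs of suicidality at the weekly meeting, or sooner when the matter is pressing.

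**The concern.** The duty and the alert sit in one paragraph but appear to have different thresholds. If ideation means at follow-up what it means at eligibility, an item 9 score of 1 calls for a risk assessment, yet it is the one positive response that the alert's item 9 criterion leaves out.

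Everyone enters with item 9 at 0 on the eligibility PHQ-9, so a score of 1 is the lowest level at which new ideation can show itself. The surveys are completed remotely, and no staff member is described as present when the answer is given. What is at stake is how promptly the team learns of a response that its own procedure appears to say must be assessed. No endpoint or estimate depends on it.

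**Working it through.** The plan states no figure here to reproduce. The check applies its rules to the possible scores.

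**Inputs**
- Nine items (section 10.0), each assumed to be scored 0 to 3. Section 5.0 codes the second response option as 1, which is consistent with this.
- Eligibility: total of at least 10 and item 9 = 0 (sections 5.0 and 9.0).
- Alert: total rise of at least 5 from baseline, or item 9 of at least 2 (section 13.0 b).
- Risk assessment: item 9 of at least 1. This is the inferred follow-up threshold.

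**When the alert fires at item 9 = 1.** Let *b* be the baseline total and *S* the follow-up sum of the other eight items, so *S* ≤ 8 × 3 = 24. Only the 5-point criterion can apply:

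*S* + 1 ≥ *b* + 5, that is, *S* ≥ *b* + 4.

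- With baseline item 9 = 0, the eight items summed to *b* at baseline. They must rise by **4 or more** in total. If they improve, stay level or worsen by up to 3 points, no described alert fires.
- The baseline PHQ-9 is not stated to be the eligibility PHQ-9, so baseline item 9 could be 1. The eight items then summed to *b* − 1 and must rise by 5 or more.

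**Ceiling.** The highest total with item 9 = 1 is 24 + 1 = 25. A rise of 5 needs *b* ≤ 25 − 5 = 20. At a baseline total of **21 or more** the 5-point criterion cannot fire, whatever item 9 was at baseline.

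**At baseline itself.** The rise is 0 by definition, so only item 9 of 2 or 3 meets the described trigger.

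**Enumeration.** Take baseline totals 10 to 24 with item 9 = 0 (15 values) and follow-up sums of the other eight items from 0 to 24 (25 values): 15 × 25 = 375 patterns for each follow-up item 9 score.

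| Follow-up item 9 | Patterns with a described alert | Patterns without |
|---|---|---|
| 1 | 66 | 309 |
| 2 | 375 | 0 |
| 3 | 375 | 0 |

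The 66 is the sum of (21 − *b*) for *b* = 10 to 20, that is, 11 + 10 + … + 1. These counts show the logic of the rule. They are not probabilities, and they do not test the inferred threshold, which was put in as an input.

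**The case against.** The strongest reply is that section 13.0 b) does define in-trial ideation. It glosses clinical deterioration as including "increasing depressive symptoms and/or the development of suicidal ideation" and then gives two criteria, the second being item 9 of 2 or 3. On that reading the follow-up threshold is 2, and alert and duty coincide. A strict bar for entry and a higher one for immediate alerts would be a coherent scheme.

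The paragraph does not fit that reading well. It attaches different actions to the two events: deterioration leads to referrals and a call a week later, whereas reported ideation leads to a risk assessment. The duty sentence also uses one term for screening and later assessments, and at screening the term means 1 or more. What stands is that carrying the eligibility threshold forward is an inference.

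Four further points also stand in part.

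- **No stated rule is breached.** The plan sets no deadline for the assessment and does not say that an automated alert must start it.
- **Detection is not absent.** A reader might infer that an item 9 score of 1 goes unwatched, or waits a week for the meeting. The documents support neither. Scores are monitored generally, urgent matters can be raised early, and no review time is given, so notice could be the same day. Other alerts may exist undescribed.
- **Contact is not barred.** Section 13.0 (Protections Against Risk) says "Should a participant evidence clinical deterioration, [name] will then use the participant database to obtain contact information". A reader might infer that contact details are available only then. The sentence does not say so, and a phone assessment already implies a look-up.
- **Prior approval.** The plan states "All risk mitigation strategies outlined have previously been approved by the MUSC IRB". That supports the procedures as a whole but does not settle which threshold applies in this text.

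**Conclusion.** The point holds as a mismatch between a stated duty and the only real-time alert described. It is an inexpensive participant-safety improvement. On the inferred threshold, a new item 9 score of 1 has no described real-time alert unless the other eight items worsen by at least 4 points in total. At baseline totals of 21 or more it can have none through the 5-point criterion.

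The conclusion assumes 0 to 3 item scoring and that item 9 of 1 or more counts as reported ideation at follow-up. The length of any delay is unstated, and the documents give no baseline score distribution or ideation rate, so the number of the 15 participants affected cannot be estimated. Nothing here supports a claim that the trial's safety monitoring has failed or that its results would be biased.

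**What to change.** Add a separate REDCap alert for any item 9 response of 1 or more, at baseline and at every follow-up PHQ-9, which prompts the phone risk assessment that section 13.0 b) already requires. State it in one or two sentences there. Leave the definition of clinical deterioration as it is, so that the rule to recruit an additional participant after deterioration is not triggered more often.

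If the team does not intend an item 9 score of 1 at follow-up to count as reported ideation, section 13.0 b) should say so and state how soon such a response is reviewed.

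The cost is one alert condition and a few more alerts to handle. The ceiling is 15 × 4 = 60 follow-up surveys plus 15 at baseline, 75 in all, plus those of any additional participants. Only surveys with item 9 = 1 and no 5-point rise would produce an alert that is not already described.

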3.0 Intervention to be studied

Moodivate: When users first download Moodivate, they complete a psychoeducational interactive tutorial, practice generating goals and activities, and receive instruction on app use. Users are then taken to their Home screen where they can see an overview of their activities for the day, plan additional activities, and track mood. Users are prompted to continuously generate new goals across life areas (Relationships, Daily Responsibilities, Recreation, Career and Education, Health) and multiple activities within each goal. By being connected to what the user values, this goal-driven framework ensures that activities will be positively reinforced³². Once a user has identified activities across goals, activities are scheduled and monitored via the Calendar (for future planning) and Home (for today) screens. After completing an activity, the user receives reinforcement (e.g., “Great job!”). Moodivate users can track daily mood to monitor progress and are prompted to complete a clinical assessment of depressive symptoms³³ once every two weeks. Users can view a graph of fluctuations in mood and depressive symptoms overlaid upon a graph of the number of completed activities, illustrating the connection between activity and mood. Users are reinforced for treatment engagement via badges³¹. Users are encouraged to use the app regularly, at least once per day, for the treatment of depressed mood³⁴. If randomized to receive Moodivate, study staff will provide the participant with a Moodivate app download code and will ensure successful download. Study staff will then give the participant a brief, scripted overview (as utilized in our R41 and R42) regarding app utilization and will provide the participant with 10 minutes to use the app and ask questions.

Figure 2: Moodivate

TAU: TAU mimics existing depression treatment for ILLIC. Participants in both conditions will be provided educational mood management material available via the EHR with the suggestion to discuss questions with their oncology provider. Across conditions, participants will not be precluded from obtaining additional treatment (e.g., pharmacotherapy, palliative care), which will be tracked throughout the study via self-report.

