4.0 Study Endpoints

Table 1. Study Objectives and Endpoints	
OBJECTIVES	ENDPOINTS
Primary: To evaluate the feasibility of conducting a RCT comparing a proactive identification + DMHI approach vs TAU among ILLIC with depression	ILLIC case identification
	Accrual
	Retention
Secondary: To determine the acceptability, appropriateness, and adoption of a proactive identification + DMHI approach among ILLIC with depression.	System Usability Scale (SUS) ³⁵ score
	Number of Moodivate app sessions
	Average time per Moodivate session
	Total time using the Moodivate app
	Number of goals created within Moodivate

Table 1. Study Objectives and Endpoints	
OBJECTIVES	ENDPOINTS
	Number of activities created within Moodivate
	Number of activities scheduled within Moodivate
	Number of activities completed
Exploratory: To explore the effect of a proactive + DMHI approach on depression, anxiety, and quality of life among ILLIC with depression relative to TAU.	Change in the PHQ-9 ³⁶ score from baseline to 1-month follow-up.
	Change in the Hospital Anxiety and Depression Scale, Anxiety subscale (HADS-A) score from baseline to 1-month follow-up.
	Change in the Functional Assessment of Cancer Therapy-General (FACT-G7) score from baseline to 1-month follow-up.

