9.0 Consent Process

After completing determination of preliminary eligibility, a member of the research team will schedule a phone call with the participant to determine final study eligibility (no suicidal ideation reported on the PHQ-9 and a score ≥ 10 on the PHQ-9). After determination of final study eligibility, a study team member will complete remote electronic informed consent (e-consent) with the participant via REDCap. Participants will receive a link to an electronic consent form, available via REDCap, that they can review and sign. Review of the consent form will be paired with a phone call with a member of the research team to ensure that all questions are answered prior to enrollment. This remote consent procedure is currently utilized across all of [name] current NIH-funded awards. As smartphone ownership is an inclusion criterion (to use Moodivate), all participants will have internet access and thus access to the electronic consent form. All participants will electronically sign informed consent forms that have been IRB-approved once the study is explained to them in full and they have stated that they understand what is being asked of them. Participants will be given the opportunity to ask questions about their participation throughout the course of the study. A copy of the informed consent will be kept centrally at our study office within locked filing cabinets and a copy will also be given to each study participant. Participants will be given a study phone number and e-mail address to contact for questions.

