10.0 Study Design / Methods

ILLIC with depressive symptoms identified chart review will be randomized 2:1 to proactive identification + DMHI vs TAU via a two-arm remote pilot feasibility RCT (N=15). The purpose of this pilot trial is to refine trial methods in preparation for a larger future grant (e.g., R01) and examine the feasibility, acceptability, and preliminary efficacy of proactive identification + self-guided DMHI approach vs TAU.

In addition to baseline assessments completed following e-consent, all participants will be text messaged and/or emailed a REDCap link, accessible via smartphone, to complete follow-ups weekly for 4 weeks. Assessments are estimated at 10 minutes each and participants will be compensated \$40 in electronic gift codes for completion of baseline assessments, \$40 for completion of each follow-up assessment, and \$100 as a bonus if all study assessments are completed. Additionally, participants will be invited to attend a post-study interview (~30-45 minutes) to help further refine trial procedures. Individual interviews may occur either remotely using an MUSC-approved HIPAA compliant video conferencing platform (e.g., Microsoft Teams, MUSC Pro Zoom) Those who participate in these interviews will earn an additional \$40 (total

potential compensation = \$340). Procedures for remote remuneration are well-established through our prior trials³⁹.

We will collect the following study measures from the EHR or patient self-report as indicated below.

Baseline Demographics (Assessed via self-report at baseline)

Participants will self-report age, race, sex, ethnicity, marital status, insurance, and home address (which will be used to determine rurality).

Clinical characteristics (Assessed via EHR data and self-report at baseline)

Clinical and mental health characteristics are assessed using clinical documentation within the EHR unless otherwise indicated.

We will collect data via the EHR and participant self-report regarding include type of cancer (breast, lung, colon, etc), type of ILLIC [locally advanced, metastatic], current cancer treatment (chemotherapy, immunotherapy, etc), and ECOG performance status⁴⁰. We will also collect self-report data regarding use of psychotherapy, pharmacotherapy, DMHIs, and supportive care services (e.g., palliative care, support groups).

Technological Experience (Assessed via self-report at baseline)

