Pew Research Center's technology adoption survey: This validated survey will be used to assess experience using technology and internet access (home broadband, access via mobile device)⁴¹.

*Mobile Device Proficiency Questionnaire (MDPQ-16)*⁴²: The MDPQ-16 is a validated 16-item measure of mobile device proficiency.

*Computer Proficiency Questionnaire (CPQ-12)*⁴³: The CPQ-12 is a validated 12-item measure of computer proficiency.

Implementation (Assessed via self-report Week 4 [SUS] and via app analytics across study duration)

*System Usability Scale (SUS)*³⁵: The SUS is a 10-item self report measure of acceptability.

Adoption: Adoption will be characterized as 1) number of app sessions, 2) average time per session, and 3) total time using the app.

Retention: Retention will be defined as any app use within each week following enrollment.

Fidelity: Fidelity will be measured as 1) number of goals created, 2) number of activities created, 3) number of activities scheduled, and 4) number of activities completed.

Clinical Efficacy (Assessed at baseline and at all study timepoints via self-report)

*PHQ-9*³⁶: The PHQ-9 is a validated 9-item measure of depression. The PHQ-9 has high sensitivity and specificity for identifying individuals with depressive symptoms, particularly among cancer survivors⁴⁴⁻⁴⁶.

*Functional Assessment of Cancer Therapy-General (FACT-G7)*⁴⁷: The FACT-G7 is a patient-reported outcome measure of health-related quality of life with good validity and reliability in patients with cancer⁴⁷.

Hospital Anxiety and Depression Scale, Anxiety subscale (HADS-A). The HADS-A is a validated 7-item patient-report measure of anxiety symptoms in the past week which has been used extensively among patients with advanced cancer⁴⁸.

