All screening information will be kept in a password protected REDCap database. Only key study personnel will have access to the database. If an individual is not eligible to participate, his/her screener will include his/her first name and last initial and the reason for disqualification. Eligible participants' full name, telephone number and e-mail address will be recorded in the database. This is the only place where participants' names and subject identification numbers appear together. Eligible participants will be assigned a subject number, will complete informed consent (see procedures above), will be randomized, will complete baseline assessments, and subsequently will receive their randomized intervention.

Upon completing eligibility screening, if study eligible, individuals will be provided with a verbal overview of the study, asked to review a consent form, and asked to provide informed consent. Participants will be informed of limitations of confidentiality (i.e., abuse or neglect, intention to harm self or someone else) both verbally and in writing during the informed consent process. The consent form will include the participant's name, but not his/her subject number. Consent forms will be provided in English. As utilization of Moodivate requires that participants are able to read, participants unable to read the consent form on their own will not be included.

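### Section 13 places randomisation before the self-reported baseline, and nothing states that allocation is withheld until baseline is submitted (minor; cheap to fix)

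*Combined protocol and SAP*

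**What the plan says.** Only one sentence in the document places randomisation relative to the baseline assessments. It is in section 13.0, under Protections Against Risk. After a subject number is assigned and consent is given, participants "will be randomized, will complete baseline assessments, and subsequently will receive their randomized intervention".

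Section 10.0 fixes the baseline only relative to consent: "In addition to baseline assessments completed following e-consent". It does not say on which side of randomisation the baseline falls.

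The PHQ-9, FACT-G7 and HADS-A are listed in section 10.0 under Clinical Efficacy as "Assessed at baseline and at all study timepoints via self-report". Table 1 in section 4.0 makes each of them an exploratory change endpoint, for example "Change in the Hospital Anxiety and Depression Scale, Anxiety subscale (HADS-A) score from baseline to 1-month follow-up".

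Delivery is open. Section 3.0 says: "If randomized to receive Moodivate, study staff will provide the participant with a Moodivate app download code". Staff then give a scripted overview and time to try the app. No section describes masking, allocation concealment, or the moment at which the arm is disclosed.

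**The concern.** A baseline score should be one that allocation cannot have affected. When it is self-reported and completed after randomisation, that holds only if the person answering, and any staff member talking to them, do not yet know the arm. Everyone enrolled has said they are willing to use an app for depressed mood (section 5.0), so learning of assignment to either arm could plausibly colour answers about mood, anxiety or quality of life.

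Two things depend on these baselines. One is the set of three exploratory change endpoints. The other is the check in section 12.0 (Quality Assurance) of whether baseline characteristics are comparable across conditions, with adjustment if needed. If allocation had already moved the baseline, that check would be examining, and possibly adjusting for, a value that is partly a result of allocation.

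**Working it through.** The plan states no figure on this point, so the check is mainly a comparison of the sections.

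**1. Order of steps.** Section 13.0 gives consent, randomisation, baseline, intervention. Section 10.0 gives consent, then baseline, and is silent on randomisation. The consent text in section 9.0, repeated in section 13.0, runs from eligibility to consent and stops there. The section 13.0 sentence is therefore the only stated order. Section 10.0 is compatible with it and equally compatible with baseline first.

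**2. When the arm becomes known.** The acts that reveal the arm are those in section 3.0: the download code, the scripted overview and the trial use of the app. They belong to delivery, which section 13.0 places after baseline. Nothing says that the arm is announced sooner, and nothing says that it is not.

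**3. What is measured before randomisation.** A PHQ-9 is used to settle eligibility before consent (section 9.0), and screening information is kept (section 13.0). It is not named as the baseline value, and no comparison with the later baseline PHQ-9 is planned. No HADS-A or FACT-G7 is described before randomisation.

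**4. Which endpoints are exposed.**
- Primary (case identification, accrual, retention): not change scores.
- Secondary (SUS score, app-use counts and times): not change scores.
- Exploratory (PHQ-9, HADS-A, FACT-G7): all three are changes from baseline to 1 month.

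**5. What an early-disclosure shift would do.** Let knowledge of the arm move the mean baseline in one arm by d points, and let b be the slope of follow-up on baseline. Through the baseline alone:
- error in the between-arm difference in change (shifted arm minus other) = −d
- error after adjusting for baseline = −b × d

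With disclosure only after baseline, d = 0 and both errors are 0. With earlier disclosure, the documents give no value for d, not even its sign, and none for b. The size and direction therefore cannot be calculated. Participants also know their arm at the weekly follow-up self-reports. Any effect of that is a separate term, which the step order neither creates nor removes.

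**6. Scale of the trial.** At 2:1 with N = 15, an exact split is 15 × 2/3 = 10 and 15 × 1/3 = 5. Section 11.0 plans mainly descriptive analysis and names no between-arm test of these three scales.

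**The case against.** The strongest reply is that the order of randomisation is not the order of disclosure. The same sentence puts receipt of the intervention after baseline, and every arm-revealing act the plan describes is part of delivery. On the natural reading, participants meet their arm after completing baseline and there is no bias. This stands as far as it goes: early disclosure is not shown. It does not remove the gap, because the plan nowhere makes that reading a requirement, and staff could follow the sentence as written and announce the arm first.

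A second reply is that the sentence sits in a paragraph about databases and subject numbers and may be loose drafting. That is possible. If so, the sentence should be corrected, since it is the only statement of order that staff have.

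A third reply is that little hangs on it: exploratory endpoints, 15 people, descriptive analysis. This also stands, and it is why the point is minor. In addition, eligibility (including the PHQ-9 threshold) is settled before consent, so entry is unaffected, and app use cannot contaminate a baseline that precedes delivery.

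A reader might go further and infer that sections 10.0 and 13.0 contradict each other. They do not, since section 10.0 fits either order.

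**Conclusion.** The point holds in a limited form. Two facts are certain: the only stated order puts randomisation before baseline, and no section withholds allocation until baseline is submitted. Any bias is conditional on the arm being known before the baseline forms are completed.

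A reader might infer that the three change endpoints are biased, or biased in favour of the app. The documents support neither inference. They do not show early disclosure, and they provide nothing from which a size or sign could be derived. If disclosure comes with delivery, the effect of the order is zero.

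Severity is minor. The primary and secondary endpoints are not change scores, and the exploratory ones will be described in about 10 and 5 people. The reason to act is the stated aim in section 10.0: "The purpose of this pilot trial is to refine trial methods in preparation for a larger future grant". Step order is one of those methods, and it would matter more in a trial that sets out to estimate the effect on these scales.

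**What to change.** In sections 10.0 and 13.0, state one order: consent, baseline assessments submitted, randomisation, disclosure of allocation, intervention. Name that pre-randomisation assessment as the baseline for the PHQ-9, HADS-A and FACT-G7 change endpoints.

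If randomisation must stay first, add one sentence saying that allocation is hidden from the participant, and from staff in contact with the participant, until the baseline forms are submitted. If baseline already comes first in practice, correct the section 13.0 sentence.

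The cost is a minor amendment, which section 12.0 says is relayed to the funding agency, and possibly a change of step order in the randomisation procedure, which the plan does not describe. No assessment is added. One consequence needs handling: with baseline first, people who consent but do not complete baseline are never randomised. They should still be reported under accrual, which is a primary endpoint. Neither version of the fix deals with participants knowing their arm at follow-up.
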